3.3 Outcome Measures

As this is a feasibility study, there are no primary outcome measures, only secondary outcome measures. These include:

- The London Classification diagnoses of each patient when rectal sensitivities are assessed using Laborie system elastic balloon distension versus the rectal barostat, and Medtronic system elastic balloon distension versus the rectal barostat.
- Percentage of rectal capacity at each sensory threshold per test will be measured to assess repeatability
- Total rectal volume (mL) measured using the rectal barostat will be recorded to assess correlation between capacity and balloon inflation (mL) at sustained urgency.
- The number of patients who were eligible to participate in the study.
- The number of patients who chose to participate in the study.
- The number of patients who dropped out of the study.
- The length of time required for the rectal barostat protocol and the elastic balloon distension protocol in clinic
- Costings of rectal barostat test comparison (costs of barostat bags and any additional staff time required)
- Study acceptability and tolerability assessment.

4.0 STUDY DESIGN

This is a feasibility study to test equivalence of elastic balloon distension to rectal barostat in diagnosing disorders of rectal sensitivity. This is a multi-site randomised study.

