3.0 OBJECTIVES AND OUTCOME MEASUREMENTS/ENDPOINTS

3.1 Primary Objective

To assess the feasibility of a definitive study which will compare two different measurement methods of rectal sensitivity. These measurement methods include the gold standard rectal barostat test and the more widely used elastic balloon distension test.

10 of 21

Study protocol: Assessing rectal sensitivity with elastic balloon distension versus rectal barostat.

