3.2 Secondary Objectives

- To assess whether they are any differences in rectal sensitivity diagnoses when using the London classification between the two methodologies (elastic balloon distension test and rectal Barostat test).
- To assess the repeatability of the rectal barostat test.
- To investigate whether patients with larger rectums require the elastic balloon to be inflated to a larger volume, before they feel an urge to defecate.
- To determine whether the Laborie elastic balloon test or Medtronic elastic balloon test aligns better with the rectal barostat test.
- To assess study participant eligibility, uptake and drop-out rate.
- To assess study acceptability and tolerability.
- To assess the costs per study of the two methodologies to help inform a definitive study (clinic time, analysis time and consumables).

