6.3 Number of Participants

In total 30 participants will be recruited for the study. 15 participants will be recruited at NuTH and 15 at CDDFT. Study recruitment will continue until complete study data has been obtained from 15 participants at each site.

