7.8 Data Analysis

To investigate whether London Classification diagnoses differs when using the rectal barostat compared to elastic balloon distension, a binary indicator will be used to determine the percentage of patients who's diagnoses were in agreement. To examine this closer, a Fisher's exact test will be used to determine whether the difference in number of diagnoses between the elastic balloon distension and rectal barostat reaches a significance level of p=0.05.

To assess repeatability of sensory thresholds at first sensation, normal urge, and sustained urgency of the rectal barostat, an intraclass correlation coefficient will be calculated for each test.

To identify whether there is a correlation between total rectal capacity and the volume of the elastic balloon at the sensory threshold of sustained urgency, a Pearson's correlation will be calculated to test the strength of the relationship between these variables.

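### Section 4.0 sets out to test equivalence, but section 7.8 gives no margin and only an unpaired test for a difference, which cannot establish it

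*Protocol*

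**What the plan says.** The design statement in section 4.0 reads: "This is a feasibility study to test equivalence of elastic balloon distension to rectal barostat in diagnosing disorders of rectal sensitivity".

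Other sections frame the same comparison differently. Section 3.1 gives the primary objective as "To assess the feasibility of a definitive study which will compare two different measurement methods of rectal sensitivity". Section 3.2 lists, as a secondary objective, whether there are "any differences in rectal sensitivity diagnoses when using the London classification between the two methodologies".

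Section 7.8 plans two analyses of the diagnoses:
- First, "a binary indicator will be used to determine the percentage of patients who's diagnoses were in agreement".
- Then, to look more closely, a Fisher's exact test of "whether the difference in number of diagnoses between the elastic balloon distension and rectal barostat reaches a significance level of p=0.05".

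On size, section 6.3 says: "In total 30 participants will be recruited for the study", split as 15 per site. Each site uses one balloon system, and section 3.3 compares each system with the barostat separately, so 15 is also an analysis size. Under section 7.4 every participant has the barostat as well as the balloon, so the diagnoses are paired.

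The protocol states no equivalence margin, minimum acceptable agreement, interval rule or power. It does not say how a non-significant p would be interpreted.

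**The concern.** Equivalence means showing that a discrepancy is smaller than some limit fixed beforehand. A test whose null hypothesis is no difference cannot do this, because failing to reject may only reflect few patients. Section 4.0 therefore states an aim that the test in section 7.8 cannot deliver.

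Fisher's exact test also misses the clinical question in two ways. It compares totals, whereas section 1.0 asks whether a given patient receives the same diagnosis from both methods. It also assumes two independent groups, whereas the same patients supply both sets of diagnoses.

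What is at stake is the reading of the main clinical comparison. Section 1.0 intends to draw an indication of the barostat's clinical utility from whether diagnoses change. A non-significant p, set beside a design labelled as an equivalence test, could be taken to show that the methods are interchangeable.

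**Working it through.** **Inputs from the protocol:** N=30, 15 per site (6.3); both tests in every patient (7.4); Fisher's exact test at 0.05 (7.8); four diagnostic categories (1.0). No margin or power is given, so there is no planned figure to reproduce.

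**Assumptions:** two-sided tests, since 7.8 does not state sidedness; two categories (hypersensitive, normal) for simplicity; illustrative shift patterns. Fisher is applied to the counts as if balloon and barostat were separate groups. For a one-way shift of *b* patients, exact McNemar gives p = 2 × 0.5^b.

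**1. One-way shifts**

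| Assumed pattern | Agreement | Counts, hypersensitive/normal (balloon vs barostat) | Fisher p | Exact McNemar p |
|---|---|---|---|---|
| 30 patients, 15 hypersensitive on balloon, 8 become normal | 22/30 = 73% | 15/15 vs 7/23 | 0.060 | 2 × 0.5^8 = 0.008 |
| The same, 9 become normal | 21/30 = 70% | 15/15 vs 6/24 | 0.029 | 2 × 0.5^9 = 0.004 |
| 15 patients, 10 hypersensitive on balloon, 6 become normal | 9/15 = 60% | 10/5 vs 4/11 | 0.066 | 2 × 0.5^6 = 0.031 |
| The same, 7 become normal | 8/15 = 53% | 10/5 vs 3/12 | 0.025 | 2 × 0.5^7 = 0.016 |

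In rows 1 and 3 the planned test is non-significant although 27% and 40% of patients change diagnosis, and the paired test detects the shift. Rows 2 and 4 show that one further change brings Fisher below 0.05.

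**2. Shifts that cancel**

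If 15 of 30 are hypersensitive by each method, the counts are 15/15 vs 15/15 and Fisher p=1.0, whether all 30 patients agree or none does. McNemar would not detect balanced changes either. Only the agreement itself shows them.

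The totals limit how far this can go. With two categories and a common proportion *q* in the larger one, agreement cannot fall below 2q − 1. At the service-evaluation rates in section 2.0 this floor is 2 × 0.914 − 1 = 83% at one site and 2 × 0.657 − 1 = 31% at the other. Zero agreement needs an even split.

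**3. What the planned numbers can show about agreement**

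With perfect agreement, the exact (Clopper-Pearson) 95% lower limit is 0.025^(1/n):
- 30/30: 0.025^(1/30) = 88.4%
- 15/15: 0.025^(1/15) = 78.2%

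With 80% agreement, 24/30 gives 61% to 92%, and 12/15 gives 52% to 96%.

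**4. Size of a paired equivalence test on one category's proportion**

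n = (z₀.₉₅ + z₀.₉₀)² × discordance / margin², with (1.645 + 1.282)² ≈ 8.56. This assumes no true difference, 80% power and one-sided alpha 0.05 for each of the two one-sided tests. Margins and discordance rates are assumed.

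| Margin | Discordance 10% | 20% | 30% |
|---|---|---|---|
| 0.10 | 86 | 172 | 257 |
| 0.15 | 39 | 77 | 115 |
| 0.20 | 22 | 43 | 65 |

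Only the most favourable cell fits within 30 patients, and none fits within 15.

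**The case against.** The strongest reply is that equivalence appears in one design sentence only. The study title asks about agreement, section 3.2 asks about differences, the primary objective is feasibility, and section 2.0 leaves the question of different diagnoses to a definitive study. On that view this is a loose label. This largely stands and is why the severity is moderate. It does not remove the conflict between sections 4.0 and 7.8.

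A second reply is that the planned percentage agreement is a within-patient measure and comes first in section 7.8. In every illustration above it would show the disagreement beside the p-value. That is correct, so Fisher is the only significance test of the diagnoses but not the only analysis. With no threshold, however, the percentage cannot decide equivalence.

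Third, intervals and table layouts are often left to a statistical analysis plan, which is not shown here. Their absence alone is no fault. The mismatch between aim and test, and the choice of an unpaired test, are written into the protocol itself.

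Two stronger readings are tempting. A reader might infer that the plan will declare equivalence when p exceeds 0.05, but no section says so. A reader might also infer that Fisher will usually be non-significant when many patients change. That is not shown: it depends on the assumed pattern, and one more change reverses both one-way examples. Low precision at this size is normal for a feasibility study and is not itself an error.

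**Conclusion.** The concern holds as an internal inconsistency of moderate severity. The aim in section 4.0 cannot be met by the test in section 7.8, because there is no margin and the test looks for a difference. The test is also wrong for paired data: under the assumed one-way shifts it returns 0.060 and 0.066 where an exact paired test returns 0.008 and 0.031. When totals match it returns 1.0 and says nothing about agreement within patients.

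These figures rest on two-sided testing, a two-category simplification and chosen shift patterns. They show what can happen, not what is likely. The main consequence is a possible misreading of a non-significant result, tempered by the planned percentage agreement and by the feasibility purpose of the study.

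**What to change.** - **Section 4.0:** replace the equivalence wording with *to estimate agreement in London Classification diagnosis*.
- **Section 7.8, main result:** keep the percentage agreement, and add an exact 95% confidence interval and the paired 4x4 table of balloon against barostat diagnosis, overall and for each balloon system.
- **Section 7.8, test:** remove Fisher's exact test. If a shift in diagnoses is to be tested, use a paired method: exact McNemar for one category against the rest, or a test of marginal homogeneity across all four.
- **Section 7.8, interpretation:** state that a non-significant result is not evidence of equivalence.
- **Definitive study:** leave the margin and the sample size to it, informed by the agreement and discordance estimated here.

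This costs a few sentences and needs no new data, patients or procedures. The downside is that the study gives up an equivalence claim. With no margin stated, and 30 patients or 15 per system, it had no sound basis for making one.

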5.0 STUDY SETTING

Multicentre study. Research sites include:

- Newcastle Upon Tyne Hospitals NHS Foundation Trust (NUTH): Royal Victoria Infirmary, Medical Physics.
- County Durham and Darlington NHS Foundation Trust (CDDFT): University Hospital of North Durham, Medical Physics.

Patients identified at each site will undergo the study at the same site. Therefore, patients are not expected to travel between sites.

6.0 PARTICIPANT ELIGIBILITY CRITERIA

6.1 Inclusion Criteria

- Aged over 18 years
- Aged under 90 years
- Male or nonpregnant female
- Meets 1 or more of the following indications for anorectal physiology investigations:
 - o Symptoms of constipation or disorder of evacuation
 - o Faecal incontinence
 - o Functional anorectal pain
 - Faecal urgency and frequency of moving bowels
 - Constant urge to move bowels
- Has had a previous lower gastrointestinal tract investigation (colonoscopy, flexible sigmoidoscopy, defecating proctogram, digital rectal examination, CT colon) in the past 2 years
- Able to understand both written and verbal English

6.2 Exclusion Criteria

- Creutzfeldt-Jakob disease
- Pregnancy
- Previous rectal surgery
- Previous pelvic radiotherapy
- Haemorrhoid banding in past 2 weeks
- Haemorrhoidectomy in past 10 weeks
- Reporting of change of bowel habits, rectal bleeding, or weight loss with no endoscopic investigations performed since symptoms commenced
- History of inflammatory bowel disease
- History of colorectal or anal cancer
- Lack of capacity to consent
- Over 90 years old
- Under 18 years old

12 of 21

Study protocol: Assessing rectal sensitivity with elastic balloon distension versus rectal barostat.

- Currently or has been involved in a clinical trial investigational medicinal product study within 6 months prior to the start of the study
- Unable to understand written and/or verbal English

6.3 Number of Participants

In total 30 participants will be recruited for the study. 15 participants will be recruited at NuTH and 15 at CDDFT. Study recruitment will continue until complete study data has been obtained from 15 participants at each site.

7.0 STUDY PROCEDURES

7.1 Recruitment

Referrals from Consultant Gastroenterologists or Colorectal Surgeons to the GI Physiology Service at NUTH or CDDFT for anorectal physiology studies will be screened for study eligibility, according to the inclusion and exclusion criteria. This will be performed by trained healthcare scientists or a trainee clinical scientist (NHS STP) under supervision. The team performing the screening and all study procedures are the same individuals that would usually be involved in the standard care of the patient.

During standard care a standard anorectal physiology patient information leaflet (PIL) and appointment letter is sent to the patient. The standard appointment letter states that the patient can call the GI physiology secretary to make an appointment for their standard anorectal physiology test or the patient can be called by the GI physiology secretary to make an appointment.

As part of the research study eligible patients will also be sent a study patient information sheet (PIS) alongside the standard anorectal physiology PIL and appointment letter. The patient will then receive a telephone call from an investigator of the research team (GI physiology team), a minimum of 5 days following postage, to determine whether they would like to participate in the study. If they are willing to participate an appointment will be made, which will include their standard clinic appointment. Full eligibility will be assessed once informed consent has been given at their clinic appointment. For patients who do not want to participate they will continue with standard care and a standard anorectal physiology appointment will be made.

7.2 Screening Logs

7.2.1 Pre-Screen Log

Participants identified by researchers who accept a PIS will be included on the prescreening log. This log will provide the following information:

- Patient initials
- Sequential screening number
- Date of when potential study eligibility was determined by researcher upon referral for anorectal physiology
- Site (NUTH or CDDFT)
- Eligibility based on clinical history (yes/no)
- Initial screening via telephone outcome (recruited, declined/reason given)
- Clinic discussion with researcher outcome (recruited, declined/reason given)

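### The pre-screen log leaves out ineligible referrals and makes the uptake denominator unclear; separately, section 6.3 fixes both 30 recruits and 15 completers per site, which agree only if nobody is incomplete

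*Protocol*

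**What the plan says.** **Screening and logging.** Under section 7.1, referrals for anorectal physiology are screened against the criteria first. After that, "eligible patients will also be sent a study patient information sheet (PIS") by post, and a telephone call follows at least five days later. Section 7.3 repeats that the sheet goes to eligible patients. Section 7.2.1 then sets the entry rule for the pre-screen log: "Participants identified by researchers who accept a PIS will be included on the prescreening log". Its fields include "Eligibility based on clinical history (yes/no") and "Initial screening via telephone outcome (recruited, declined/reason given"), with a matching field for the clinic discussion. The identification log in section 7.2.2 covers recruited participants only, and it records withdrawals with time and reason.

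**What the logs must support.** Section 3.2 makes eligibility, uptake and drop-out an objective. Section 3.3 gives the outcomes as counts, for example "The number of patients who were eligible to participate in the study", with no denominator.

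**Numbers.** Section 6.3 states: "In total 30 participants will be recruited for the study". It continues: "15 participants will be recruited at NuTH and 15 at CDDFT". It ends: "Study recruitment will continue until complete study data has been obtained from 15 participants at each site".

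**The concern.** There are two separate defects.

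First, the log's entry rule comes after the eligibility decision it is meant to record. Someone found ineligible is never sent a PIS and so cannot accept one. The eligibility field will be yes for nearly every row. The word 'accept' also fits badly with a sheet sent by post, because no step before the telephone call lets a patient accept it. One site could log everyone posted a sheet and the other only those who show interest, and their uptake figures would then not be comparable.

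Second, section 6.3 gives a recruitment total and a stopping rule that differ as soon as one participant is incomplete. The protocol allows for this. Drop-out is an outcome (3.3), tests may be abandoned (2.1), consent may be withdrawn at any point (7.3, 7.6), and full eligibility is checked only after consent (7.1).

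At stake are the figures a feasibility study exists to hand on: how many referrals qualify, how many of those join, and how many must be recruited to obtain a given number of complete datasets. A referral that was not logged cannot be reliably counted afterwards, so this cannot be left to the analysis stage.

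**Working it through.** **1. Who reaches the pre-screen log** (sections 7.1, 7.2.1, 7.2.2 side by side)

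| Referral | Sent a PIS? | In the log? |
|---|---|---|
| Screened, ineligible | No | No |
| Eligible, not reached by telephone | Yes | Unclear; no outcome code fits |
| Eligible, declines by telephone | Yes | An outcome code exists; entry depends on 'accept' |
| Agrees by telephone, declines in clinic | Yes | Yes, with reason |
| Consents | Yes | Yes, and in the identification log |

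**2. Proportion eligible.** The wanted figure is eligible ÷ screened. The log holds no ineligible referrals, so it can give only eligible ÷ eligible, about 100%. That is the same answer whether the true proportion is 30% or 90% (assumed range). No other log described in the protocol holds the number screened.

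**3. Uptake.** Let u be the true uptake among those sent a PIS, and m the share of those sent a PIS who are not logged. All who consent are logged, so

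apparent uptake = u ÷ (1 − m).

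The protocol gives neither u nor m. Taking u = 40% as an assumption:

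- m = 0: 0.40 ÷ 1.00 = 40%, no distortion
- m = 10%: 0.40 ÷ 0.90 = 44%
- m = 20%: 0.40 ÷ 0.80 = 50%
- m = 50%: 0.40 ÷ 0.50 = 80%

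**4. The recruitment number.** The stated total reproduces as a sum: 15 + 15 = 30. The protocol gives no power, precision or drop-out input behind it. Let d be the proportion of recruits without complete data (assumed, since none is stated). Under the completer rule, expected recruits = 30 ÷ (1 − d). The spread is negative binomial with 30 completions required. The chance that exactly 30 recruits suffice is (1 − d)^30. If recruitment stopped at 30 instead, expected completers would be 30 × (1 − d).

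| Assumed d | Expected recruits (rounded up) | 5th–95th percentile | Chance 30 suffice | Completers if stopped at 30 |
|---|---|---|---|---|
| 5% | 31.6 (32) | 30–34 | 0.21 | 28.5 |
| 10% | 33.3 (34) | 31–37 | 0.04 | 27 |
| 15% | 35.3 (36) | 32–40 | 0.008 | 25.5 |
| 20% | 37.5 (38) | 33–43 | 0.001 | 24 |
| 30% | 42.9 (43) | 36–50 | <0.001 | 21 |

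The two statements in 6.3 agree only at d = 0.

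**5. Does the completer rule distort the drop-out estimate?** If every recruit is counted, incomplete ÷ recruited averages 9.7% at a true 10% and 19.5% at a true 20%. The bias is under one percentage point.

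**The case against.** The strongest reply on the log is that 'accept' is only loose wording. The log has a code for declining at both the telephone and clinic stages, which would make little sense if entry already required agreement. It also records the date eligibility was determined at referral. On that reading everyone sent a PIS is logged and the uptake denominator is nearly complete. Section 3.3 asks only for the number eligible, which such a log supplies. This largely stands. A reader might infer that the protocol builds in inflated uptake, but the text does not establish that; it depends on who is left off. Two gaps remain on either reading: ineligible referrals are absent, and a patient who never answers the telephone has no code.

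On 6.3, the reply is that its last sentence shows 15 completers per site is meant, so only the wording needs repair. That is fair as to intent. Even so, the headline total then understates likely recruitment, no cap is set, and completeness is undefined. It is unclear, for instance, whether an unreturned questionnaire (7.5.5) would trigger a further recruit.

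A reader might also infer that replacing incomplete participants inflates eligibility or uptake. It cannot, because replacement happens after both are settled. Nor do the documents support inferring that only completers are analysed, and hence that the most and least sensitive patients are lost. Section 6.3 says when recruitment stops, not who is analysed. Section 7.6 keeps non-identifiable data up to withdrawal, and section 7.8 defines no completers-only set. The handling of incomplete tests may properly sit in an analysis plan that is not shown.

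**Conclusion.** Both defects hold, as separate points. As written, the log cannot yield the proportion of referrals eligible. This follows from the text and needs no assumption. The uptake denominator is ambiguous: the distortion is nil if everyone sent a PIS is logged, and a true 40% would read 44% to 50% if 10% to 20% of them were not. Those shares are illustrations, not estimates.

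The two statements in 6.3 conflict unless nobody is incomplete. At an assumed 10% or 20% incomplete, about 34 or 38 recruits are expected against the stated 30. The drop-out estimate is barely affected, provided all recruits are counted. The point concerns planning information for the definitive study and does not reach the validity of the comparison between the two tests. It is worth correcting because the missing denominator cannot be rebuilt later and the correction is cheap.

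**What to change.** **Section 7.2.1.** Enter every referral screened at each site, anonymised, with eligibility yes/no and the reason if no. Replace 'accept' with 'are sent'. Add *not contactable* to the telephone outcomes.

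**Sections 3.2 and 3.3.** Report the three figures as proportions with stated denominators: eligible out of screened, consented out of those sent a PIS, and dropped out of all recruited.

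**Section 6.3.** Replace the three sentences with wording such as: *30 participants with complete data, 15 per site; more than 30 may be recruited, up to a stated cap.* Define complete study data, including whether the questionnaire counts. State that all recruits enter the uptake and drop-out figures. Align the planned sample size in the Study Summary.

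**Cost.** One log row per referral, for screening that is already being done, and a wording amendment. The stated recruitment ceiling rises above 30.
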